14.1. Treatment Outcome

(SCY-078-206 Protocol Amendment 5, 13 October 2020 Section 19.7.1.1)

Global Response will be assessed *at Day 42, Day 84 (if applicable) and at EOT*, based on the following definitions,:

Global Response:

- Complete Response: Survival and resolution of all attributable symptoms and signs of disease; plus, successful radiological outcome; plus, documented mycological eradication of infected sites that are accessible to repeated sampling or presumed eradication of sites that are not accessible to repeated sampling.
- Partial Response: Survival and improvement of attributable symptoms and signs of disease; plus at least 25% reduction in diameter of radiological lesion(s); plus, documented mycological eradication of infected sites that are accessible to repeated sampling or presumed eradication of sites that are not accessible to repeated sampling. In cases of radiological stabilization (defined as 0%-25% reduction in the diameter of the lesion), resolution of attributable symptoms and signs of fungal disease, *including serum GMI (for patients with positive GMI at baseline), can be equated with a partial response. In cases of radiological stabilization, biopsy of an infected site (e.g., lung biopsy) showing no evidence of hyphae and negative culture results can be equated with a partial response.
(* applicable for DRC assessments)
- Stable response: Survival and no improvement in any attributable symptoms and signs of disease; plus, radiological stabilization (defined as a 0%-25% reduction in the diameter of the lesion); or persistent isolation of mold or histological presence of invasive hyphae in infected sites.
- Progression of disease: Worsening clinical symptoms and signs of disease; plus, new sites of disease or radiological worsening of preexisting lesions; or persistent isolation of mold species from infected sites.
- Death: Death during the prespecified period of evaluation regardless of attribution.

Clinical, mycological and radiological outcome will be assessed *at Day 42, Day 84 (if applicable) and at EOT*, based on the following definitions:

Clinical response

- Success:
 - Resolution of all attributable clinical symptoms and physical findings
 - Partial resolution of attributable clinical symptoms and physical findings
- Failure:
 - No resolution of any attributable clinical symptoms and physical findings and/or worsening
- Not applicable:
 - No attributable signs and symptoms present at Baseline and no symptoms attributable to invasive fungal disease developed post Baseline

Mycological response

- Success:
 - Eradication
 - Presumed eradication
- Failure:
 - Persistence
 - Presumed persistence
- Not applicable:
 - No mycological evidence available at Baseline

Radiological response

Day 42:

- Success (improvement of at least 25% from Baseline)
- Failure
- No post Baseline radiology available for patient with baseline evidence of radiological disease
- Radiology not applicable at Baseline

Day 84:

- Success (improvement of at least 50% from Baseline)
- Failure
- No post Baseline radiology available for patient with baseline evidence of radiological disease
- Radiology not applicable at Baseline

EoT:

- Success (improvement of at least 25% from Baseline if EoT occurs prior to Day 42; if EoT occurs after Day 42, at least 50% improvement from Baseline)
- Failure
- No post Baseline radiology available for patient with baseline evidence of radiological disease
- Radiology not applicable at Baseline

Recurrence, at 6-week FU visit

Recurrence is defined as a diagnosis of probable or proven IPA (based on EORTC) after EoT in patients who have previously achieved complete response. Re-emergence of the *Aspergillus* infection is required to be with the same species (if *Aspergillus* isolates are available for both the baseline and the recurrent episode) and involving the same site that was initially identified at Screening.

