10.2 Secondary Endpoints

Efficacy as measured by:

- Global Response as measured by:
 - Percentage of subjects with Complete Response or Partial Response at EoT (key secondary endpoint), Day 42 and Day 84, as determined by the DRC
 - Percentage of subjects with Complete Response or Partial Response at EoT, Day 42 and Day 84, as determined by the Principal Investigator
- Overall survival, defined as the time from randomization to time of death up to Day 84
- Percentage of subjects who died (any cause) at Days 42 and 84

- Absolute reduction and percent change in serum GMI from Baseline to Weeks 1, 2, 4 and 6
- Percentage of subjects with the following changes in serum GMI from Baseline:
 - Fifty percent reduction or greater at Weeks 1, 2, 4 and 6
 - Twenty-five percent reduction or greater at Weeks 1, 2, 4 and 6
 - Any percent reduction at Weeks 1, 2, 4 and 6
 - Reduction equal to or greater than 0.25 at Weeks 1, 2, 4 and 6
 - Reduction to < 0.5 at Weeks 1, 2, 4 and 6
- Time to achieve the following changes in serum GMI from Baseline:
 - Fifty percent reduction
 - Twenty-five percent reduction
 - Any percent reduction
 - Reduction equal to or greater than 0.25
 - Reduction to < 0.5 in 2 consecutive samples
- Percentage of subjects with:
 - Clinical Response at EoT, Day 42 and Day 84, as determined by the DRC
 - Mycological Response at EoT, Day 42 and Day 84, as determined by the DRC
 - Radiological Response at EoT, Day 42 and Day 84, as determined by the DRC
- Percentage of subjects with:
 - Clinical Response at EoT, Day 42 and Day 84, as determined by the Principal Investigator
 - Mycological Response at EoT, Day 42 and Day 84, as determined by the Principal Investigator
 - Radiological Response at EoT, Day 42 and Day 84, as determined by the Principal Investigator

PK as measured by:

• SCY-078 and voriconazole plasma concentrations population PK analysis

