19.7.1.1 Treatment Outcome

Global Response will be assessed based on the following definitions:

- Global Response
 - Complete Response: Survival and resolution of all attributable symptoms and signs of disease; plus, successful radiological outcome; plus, documented mycological eradication of infected sites that are accessible to repeated sampling or presumed eradication of sites that are not accessible to repeated sampling.
 - Partial Response: Survival and improvement of attributable symptoms and signs of disease; plus at least 25% reduction in diameter of radiological lesion(s); plus, documented mycological eradication of infected sites that are accessible to repeated sampling or presumed eradication of sites that are not accessible to repeated sampling. In cases of radiological stabilization (defined as 0%-25% reduction in the diameter of the lesion), resolution of attributable symptoms and signs of fungal disease can be equated with a partial response. In cases of radiological stabilization, biopsy of an infected site (e.g., lung biopsy) showing no evidence of hyphae and negative culture results can be equated with a partial response.
 - Stable response: Survival and no improvement in any attributable symptoms and signs of disease; plus, radiological stabilization (defined as a 0%-25% reduction in the diameter of the lesion); or persistent isolation of mold or histological presence of invasive hyphae in infected sites.
 - Progression of disease: Worsening clinical symptoms and signs of disease; plus, new sites of disease or radiological worsening of preexisting lesions; or persistent isolation of mold species from infected sites.
 - Death: Death during the prespecified period of evaluation regardless of attribution.

Clinical, mycological and radiological outcome will be assessed based on the following definitions:

- Clinical response
 - Success:
 - Resolution of all attributable clinical symptoms and physical findings
 - Partial resolution of attributable clinical symptoms and physical findings
 - Failure:

- No resolution of any attributable clinical symptoms and physical findings and/or worsening
- Not applicable:
 - No attributable signs and symptoms present at Baseline and no symptoms attributable to invasive fungal disease developed post Baseline
- Mycological response
 - Success:
 - Eradication
 - Presumed eradication
 - Failure:

- Persistence
- Presumed persistence
- Not applicable:
- No mycological evidence available at Baseline

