8.1. Key Efficacy Endpoint and Analysis

The key efficacy endpoint is the assessment of Global Response as determined by the DRC.

The DRC will assess the Global Response at Day 42, Day 84 and EoT.

Analysis of Global Response by the DRC will be for the ITT Population.

Global Response will be summarized at each visit.

In addition, the percentage of subjects with a Global Response, defined as either a complete or partial response at EoT, Day 42 and Day 84 will also be summarized. Subjects with missing data at EoT, Day 42 and Day 84 will be considered as indeterminate response at the corresponding visit. The response rate will be calculated for each treatment group as the number of successes divided by the total number of patients (success + failure + indeterminate).

The difference in response rates between treatments will be presented along with a 95% confidence interval (CI) calculated using the wmethod of Clopper-Pearson.

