8.2.13. Time to Achieve a 10-Point Improvement in Karnofsky Score from Baseline

Time to achieve a 10-point improvement in Karnofsky score from baseline will be expressed in days and calculated using the formula:

$$\text{Time to Achieve} = \text{Date of Achievement/Censoring} - \text{Date of Randomization.}$$

Subjects not achieving the 10-point improvement by Day 84 will be censored at their last Karnofsky assessment date, date of withdraw, date of death or at Day 84 whichever comes first.

The number and percentage of subjects with events and censored will be summarized.

The Kaplan-Meier method will be used to estimate the distribution of time to achieve target for each treatment group. The 25th percentile, median and 75th percentile and their 95% CIs will be presented.

8.2.14. Percentage of Subjects with a Recurrence of the Baseline Fungal Infection within 42 Days (Week 6) after EoT

Assessment of recurrence of the baseline fungal infection will take place at the follow-up visit, 6 weeks after EoT.

The percentage of subjects with a recurrence will be summarized, by treatment, for the ITT Population. The denominator for the percentage will be the number of subjects without the baseline fungal infection at EoT.

8.2.15. Relationship Between Serum GMI Decrease and ACM at Days 42 and 84 for subset of patients with positive serum galactomannan at baseline

At Day 42, subjects will be categorized as dead or alive. For each of these two groups of subjects, a boxplot will be presented showing their last available GMI decrease, up to and including Day 42. Should a subject have no post baseline GMI data then they will not be included in the plot. The plot will be based on the ITT Population.

The above plot will be repeated for Day 84.

8.2.16. Relationship between serum GMI decrease and global response at D42 and EOT for subset of patients with positive serum GM at baseline**8.2.17. Relationship between serum GMI decrease and clinical response at D42 and EOT for subset of patients with positive serum GM at baseline****8.2.18. Relationship between serum GMI decrease and radiological response at D42 and EOT for subset of patients with positive serum GM at baseline****8.2.19. Number of subjects with complete response and alive at Day 42 and at Day 84****8.2.20. Days of Hospital Stay and Days of ICU Stay**

For each subject the number of days of hospital stay and the number of days of ICU stay will be calculated.

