10.7. Physical Examination

A general physical examination is done at Screening, Day 1, Day 14, Day 28, Day 42, Day 56, Day 70, Day 84, EoT and at Follow-Up.

Physical examination results will be summarized, by treatment, for the Safety Population.

11. Interim Analyses

The protocol planned for the performance of an interim analysis. However, there is no interim analysis since the study was stopped after enrolment of 22 subjects, due to patient recruitment challenges..

12. Changes from Analysis Planned in Protocol

There are currently no deviations from the analyses planned in the protocol. Enrollment into the study was stopped after 22 subjects were randomized because of the subject recruitment challenges and feasibility to enrol the planned sample size of 60 subjects.

13. Programming Considerations

All tables, figures, listings (TFLs), and statistical analyses will be generated using SAS for Windows, Release 9.4 or higher (SAS Institute Inc., Cary, NC, USA). Computer-generated table, listing and figure output will adhere to the following specifications.

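### SAP 14.1 adds a serum GMI condition to the DRC's Partial Response that protocol 19.7.1.1 does not contain, and SAP Section 12 does not declare it

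*SAP*

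**What the plan says.** Protocol 10.2 defines the key secondary endpoint through the DRC's assessment, in this wording: "Percentage of subjects with Complete Response or Partial Response at EoT (key secondary endpoint), Day 42 and Day 84, as determined by the DRC". SAP 8.1 agrees: "The key efficacy endpoint is the assessment of Global Response as determined by the DRC".

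Partial Response can be reached in more than one way. For a subject whose lesions are radiologically stable, protocol 19.7.1.1 (and the synopsis in the same terms) states that "resolution of attributable symptoms and signs of fungal disease can be equated with a partial response". GMI is not mentioned, and one definition serves both the DRC and the investigator.

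SAP 14.1 gives its source as "SCY-078-206 Protocol Amendment 5, 13 October 2020 Section 19.7.1.1". At the same place in the definition, after the symptoms and signs, it reads "including serum GMI (for patients with positive GMI at baseline), can be equated with a partial response". An asterisk limits the insertion: "applicable for DRC assessments".

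SAP Section 12, which is there to record changes, states: "There are currently no deviations from the analyses planned in the protocol". SAP 8.2.16 plans an exploratory analysis under the heading "Relationship between serum GMI decrease and global response at D42 and EOT", restricted to subjects with positive serum galactomannan at baseline. It gives no method and names no assessor.

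**The concern.** A reader who follows the SAP's citation will take its response definition to be the protocol's. It is not. A DRC case with stable imaging, resolved symptoms and persisting serum GMI is a Partial Response under the protocol and not under the SAP. Three things follow.

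- The key efficacy result would be reported under a definition that the protocol does not contain, with a statement that nothing changed.
- DRC and investigator response rest on different definitions, although SAP 8.2.1 analyses the second exactly as the first. Anyone reading the two rates side by side would attribute to judgement what may come from the rule.
- Serum GMI decrease is already a secondary endpoint in its own right. Placing GMI inside the response carries any GMI difference into the key endpoint, and may build part of the 8.2.16 association in by definition. Protocol 8.2 says the study should guide the choice of Phase 3 endpoints, so this association could inform that choice.

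**Working it through.** The plan has no sample size, alpha or power figure to reproduce. The check is a comparison of texts, followed by arithmetic on what one subject is worth.

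**Texts side by side (stable imaging, symptoms and signs resolved)**

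| | Protocol 19.7.1.1 | SAP 14.1, DRC | SAP 14.1, investigator |
|---|---|---|---|
| Serum GMI negative at baseline | Partial Response | Partial Response | Partial Response |
| Serum GMI positive at baseline, resolved | Partial Response | Partial Response | Partial Response |
| Serum GMI positive at baseline, not resolved | Partial Response | not by this route | Partial Response |

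Only one cell differs. Complete Response, the route through a reduction of at least 25%, and the biopsy route are the same in both documents. The clause is an added condition, so it can remove DRC responders but cannot create any.

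**Who falls under it.** SAP 8.1 analyses the ITT population. Protocol 22.3 allows probable IPA on BAL GMI, cytology, microscopy, culture or PCR as well as on serum GMI, so the ITT population can hold subjects inside and outside the clause. The documents do not give the share with positive serum GMI.

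**What one subject is worth.** SAP 3.4 gives about 22 randomized, 11 per arm.
- 1/11 = 9.1 percentage points; 2/11 = 18.2 points; 0/11 = 0.
- At the 10 per arm stated in SAP 3.7: 1/10 = 10.0 points. At the 30 per arm first planned: 1/30 = 3.3 points.

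**Illustration with assumed inputs.** Among subjects with positive serum GMI at baseline, let a be the share who respond by other routes, s the share who can respond only by this route, and g the share whose GMI resolves, taken as independent of route. None of these is in the documents; the ranges are s = 0.10 to 0.30 and g = 0.5 to 0.9.
- Response rate: a + s under the protocol, a + s·g under the SAP. Drop = s(1 − g).
- Smallest drop: 0.10 × 0.1 = 1 point. Largest: 0.30 × 0.5 = 15 points.
- Expected number reclassified among 11 such subjects: 11 × 0.10 × 0.1 = 0.11, up to 11 × 0.30 × 0.5 = 1.65.
- Response among subjects with resolved GMI minus response among those without: under the protocol (a + s) − (a + s) = 0; under the SAP (a + s) − a = s, that is 10 to 30 points.
- If GMI resolution differed between arms by 20 to 40 points, the clause alone would give an arm difference in DRC response of s × (difference in g): 0.10 × 0.20 = 2 points, up to 0.30 × 0.40 = 12 points.

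In the whole ITT population, the drop and the arm difference shrink in proportion to the share with positive serum GMI. The association figure concerns GMI resolution. Section 8.2.16 uses GMI decrease, so it inherits the effect only as far as decrease and resolution coincide.

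**The case against.** The strongest reply is that the protocol foresaw this. Its Appendix C (22.3) says that a DRC charter will set out the detailed criteria for outcome analysis and will record the DRC's adaptations of the EORTC-MSG criteria. Limiting the clause to the DRC also has a plausible reason: under protocol 15.15, serum GMI after randomization is measured centrally and sites do not see it in real time, although they may order local tests. The asterisk makes the insertion visible. All of this stands, and it means that the rule itself cannot be called wrong. It does not repair the citation, which names protocol 19.7.1.1 and not a charter, or the statement in Section 12.

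Protocol 15.21 also lists serum GMI among the mycological tests used to assess outcome, so GMI may reach the response through the mycological component regardless of the clause. That is correct, and it limits what removing the clause from 8.2.16 can achieve. It does not make GMI resolution a condition of the stabilization route.

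A reader might infer more than the documents support:
- **That the reported endpoint is not the registered one.** No registry record is at hand; only the protocol definition can be compared.
- **That 8.2.16 is circular outright.** It names no assessor. If it uses the investigator's response, the clause does not apply.
- **That the DRC rate shifts by 9 to 18 points.** That presumes one or two reclassified subjects. The count could be zero.
- **That the treatment comparison is biased.** No difference between arms in GMI resolution has been shown in these patients.
- **That the investigator comparison is invalidated.** No concordance analysis is planned; each assessor's response is compared between arms separately.

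**Conclusion.** The discrepancy is established by the text. SAP 14.1 adds a GMI condition for DRC assessments that its cited source lacks. The condition alters the definition behind the key secondary endpoint and separates it from the investigator's. Section 12 is therefore inaccurate.

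The size is bounded by structure, not known: one route to Partial Response, one direction, and 9.1 points per reclassified subject in an arm of 11, with an unknown count that may be none. The 1 to 15 point drop and the 10 to 30 point built-in association rest wholly on assumed shares and on independence of GMI resolution and route. The association point is conditional on 8.2.16 using the DRC response; if it does, it applies in exactly the subset that the clause governs.

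Section 14.1 also gives no threshold or sampling rule for GMI resolution, although 8.2.5 and 8.2.6 list several possible targets, so two readers could apply the clause differently. Efficacy is secondary and exploratory here, so this should be corrected before reporting but does not undermine the primary safety objective.

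**What to change.** - **Section 12:** list the clause as a change from protocol 19.7.1.1, with its source (for example the DRC charter, if it is there) and its date relative to unblinding. Correct the citation in 14.1 to match.
- **Definition:** state which serum GMI threshold and which sample or samples count as resolution.
- **Reporting:** have the DRC flag each case decided by the clause, and present DRC Global Response with and without it at EoT, Day 42 and Day 84. If the charter holds the rule, that version leads; otherwise the protocol definition leads.
- **Section 8.2.16:** name the assessor, run the analysis on the response without the clause, and note that serum GMI may still enter through the mycological component.

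The cost is SAP wording, one flag for the cases concerned and one extra table. No new data collection is needed.

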14.2. PopPK analysis plan
